Model Unadjusted				
Intervention Arm:	STOP Taking hypertonic saline [1, 2]			
Model Adjusted for Randomization Strata				
Intervention Arm:	STOP Taking hypertonic saline [2, 3]			
Randomization Strata:	FEV ₁ % Predicted ≥90% [4] On both HS and Dnase [5] Prior study enrollment [6] Age ≥18 years [7]			

[1] The overall unadjusted intervention arm difference (STOP Taking - KEEP Taking) is estimated using a two-sample t-test.

[2] Compared to reference level, KEEP taking **hypertonic saline**.

[3] Least Squares Mean Estimates from model with weighting proportional to observed frequencies of randomization factor combinations in the data.

[4] Compared to reference level, FEV₁ % Predicted < 90% at Week 0 (Visit 1).

[5] Compared to reference level, one therapy at Week -2 (Screening).

[6] Compared to reference level, no prior study enrollment.

[7] Compared to reference level, age <18 years at Week 0 (Visit 1).

[8] Missing values are imputed using the least favorable treatment mean in arms discontinuing treatment and using most favorable treatment mean in arms continuing treatment.

[9] Two-sided p-value.

12 Listings

Listing 12.1. Protocol Violations and Deviations

Participant ID	Intervention Arm	Description	Protocol Reference	Category	Violation Issued?	Corrective Action Required?	Corrective Action Specify	Date of Action	IRB Notification Required?	Date of Notification
----------------	------------------	-------------	--------------------	----------	-------------------	-----------------------------	---------------------------	----------------	----------------------------	----------------------

Listing 12.2. Pregnancies

Participant ID	Intervention Arm	Description	Start Date	End Date	Outcome
----------------	------------------	-------------	------------	----------	---------

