14.5 Analysis of Exploratory Objectives

Differences between treatment arms in the change in MCC from randomization to week 6 will be estimated using general linear regression adjusting for randomization strata and reported with associated confidence intervals. The average impact score on subject perception of how stopping HS or dornase alfa (or both) would impact daily life will be summarized at week 6 by treatment arm.

Among those enrolled in the lower lung function cohort, descriptive safety summaries will be provided for the differences between treatment arms in the change in FEV₁ % predicted, AE rates, and proportion

of subjects re-initiating therapy in the discontinuation arm. Treatment arms will be formally compared within this cohort as further specified in the SAP to determine if discontinuation of therapy results in clinically meaningfully inferior outcomes as compared to remaining on therapy.

Among those who are currently taking both hypertonic saline and dornase alfa at study entry, exploratory analysis will be performed pooling data across studies. Data from the arms randomized to remain on therapy in both Study A and Study B will be pooled to form a single comparator arm of subjects on both hypertonic saline and dornase alfa across trials. This comparator arm will be compared separately to the subgroups of subjects in each study randomized to discontinue therapy using the same methodology as for the primary objective.

The proportions of subjects remaining on and off hypertonic saline and dornase alfa for up to 24 weeks after completion of each study will be descriptively summarized. The odds of staying with the same regimen as assigned during the previously completed study will be modeled using logistic regression for each treatment arm with covariates derived from both baseline and clinical outcome data during the study. Data across studies may be pooled into the same model and repeated measures methodology utilized. Similar methodology will be used to summarize and model the proportion of subjects with acute antibiotic use after completion of each study.

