3.2.4. Adverse Events

All reported SAEs and AEs are coded using MedDRA and grouped by system organ class (SOC). The number of (S)AEs is summarized by each intervention arm as follows: (i) The proportion of participants with at least one (S)AE, (ii) The average number of (S)AEs per participant, and (iii) The rate of (S)AEs per participant week of follow-up. Histograms showing the frequency of the number of (S)AEs in each intervention arm are included. The incidence and rate of (S)AEs in each intervention arm is summarized by SOC and preferred term, relationship to arm, and severity. Poisson regression modeling is used to derive rate ratios and 95% confidence intervals. Rates by arm are compared using a two-sided 0.05 level test for Poisson count data. Proportions of participants with at least one (S)AE are also compared between arms with estimated differences and corresponding 95% confidence intervals by the Newcombe-Wilson method without continuity correction; p-values are from a two-sided 0.05 level Fisher's Exact test.

The number and percent of participants changing their assigned therapy due to an adverse event is summarized by intervention arm. The number and percent of participants changing their assigned therapy when directed by a physician because of an adverse event is also summarized.

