3.2.13. Lower Lung Function (LLF) Cohort

The lower lung function cohort monitoring and outcomes will be summarized in a separate report from Study A. Among those enrolled in the lower lung function cohort, descriptive safety summaries will be provided for the differences between treatment arms in the change in FEV1 % predicted, adverse event rates, and proportion of participants non-adherent to assigned therapy after randomization. Non-adherence will include definitions based on three distinct outcomes: a change action relative to assigned treatment following an adverse event, <70% adherence overall post-randomization, and <70% adherence in the last 2 weeks prior to Week 6. Treatment arms will be formally compared within this cohort to determine if assignment to STOP Taking

hypertonic saline results in clinically meaningfully inferior outcomes as compared to the KEEP Taking hypertonic saline. The primary analysis population will be ITT, with PP analyses reported if indicated for sensitivity. For all analyses with a model adjusted for randomization strata, the only stratification variable included is treatment combination at screening.

The following exhibits will be excluded from the LLF reports:

Screening Tables 1.2 and 3.1. Screening Figure 2.1. Study Figure 3.1. Also, Study Table 6.1 and Figure 6.1 will be excluded from interim reports.

The following are other modifications to the LLF report exhibits:

Screening exhibits remove components referencing Study B or use of dornase alfa only, which are not applicable to the LLF cohort. Screening tables present overall summaries only (i.e., do not include columns further broken down by treatment regimen and prior enrollment).

Demographic summaries remove the age category of ≥ 12 to < 18 years and modify the FEV₁ % predicted categories (< 40 , ≥ 40 to < 50 , ≥ 50 to < 60 , > 60). Study Table 4.11 also uses modified FEV₁ % predicted categories (< 50 , ≥ 50).

SIMPLIFY
Overview of SIMPLIFY Enrollment Across Studies
Final Report

PROTOCOL NUMBER:	SIMPLIFY-IP-19
PROTOCOL TITLE:	A Master Protocol to Test the Impact of Discontinuing Chronic Therapies in People with Cystic Fibrosis on Highly Effective CFTR Modulator Therapy (SIMPLIFY)
PRINCIPAL INVESTIGATORS:	[name] University of Washington/Seattle Children's [name] University of Washington/Seattle Children's [name] Dartmouth-Hitchcock Medical Center
FUNDING AGENCIES:	Cystic Fibrosis Foundation, Inc. (CFF)

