	Mean (SD)		
	Median		
	Min, Max		
≥70% Adherence Overall from Week 0 to Week 6	n (%)		
≥70% Adherence in Last 2 Weeks Prior to Week 6	n (%)		
≥70% Adherence Overall and in Last 2 Weeks Prior to Week 6	n (%)		

[1] Adherence for each participant is defined as Y/X , multiplied by 100, where X is the number of days participant submitted the questionnaire and Y is the number of days participant followed treatment assignment.

[2] Two weeks prior to Week 0 includes questionnaires from the 13 days prior to Week 0 (Visit 1) as well as a 14th questionnaire if and only if completed on day of visit.

[3] Excludes participants who withdrew prior to the end of the window for Week 6.

[4] Excludes participants who withdrew prior to the end of the window for Week 6 or had no submissions in the last 2 weeks period (i.e., adherence not calculable).

Table 3.4. ETI Adherence

This table summarizes therapy adherence for elexacaftor/tezacaftor/ivacaftor (ETI) from Week 0 (Visit 1) to Week 6 (Visit 3) among subjects who have completed study or withdrawn. Adherence in this table is based on the ePRO daily study adherence questionnaire. Only randomized participants for whom we have questionnaire submissions for will be considered evaluable for this table.

	STOP Taking (N=)	KEEP Taking (N=)	Total (N=)
Intent to Treat Population			
Number of Daily Submissions from Week 0 to Week 6			
N			
Mean (SD)			
Median			
Min, Max			
ETI Adherence from Week 0 to Week 6 [1], %			
N			
Mean (SD)			
Median			
Min, Max			
Number of Daily Submissions in Last 2 Weeks Prior to Week 0 [2]			
N			
Mean (SD)			
Median			
Min, Max			
ETI Adherence in Last 2 Weeks Prior to Week 0 [1,2], %			
N			
Mean (SD)			
Median			
Min, Max			
Number of Daily Submissions in Last 2 Weeks Prior to Week 6 [3]			
N			
Mean (SD)			
Median			
Min, Max			
ETI Adherence in Last 2 Weeks Prior to Week 6 [1,4], %			
N			
Mean (SD)			
Median			
Min, Max			
Difference in ETI Adherence in Last 2 Weeks (Prior to Week 6 – Prior to Week 0) [1,2,4], %			
N			
Mean (SD)			

	Median			
	Min, Max			
≥70% Adherence Overall from Week 0 to Week 6				
	n (%)			
≥70% Adherence in Last 13 Days Prior to Week 6 [4]				
	n (%)			
≥70% Adherence Overall and in Last 13 Days Prior to Week 6 [4]				
	n (%)			
Per Protocol Analysis Population				
Number of Daily Submissions from Week 0 to Week 6	N			
	Mean (SD)			
	Median			
	Min, Max			
ETI Adherence from Week 0 to Week 6 [1], %				
	N			
	Mean (SD)			
	Median			
	Min, Max			

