This table summarizes the proportion of participants changing their assigned therapy regimen (i.e., participants restarting hypertonic saline therapy in 'stop taking' arm and participants stopping hypertonic saline therapy in 'keep taking' arm) due to an adverse event (AE). Also summarized are those that were physician directed to change their assigned therapy regimen.

	STOP Taking (N=x)	KEEP Taking (N=x)	Difference in proportions (95% CI)[1]	P-value [2][Final Report Only]
Total number of AEs				
Total number (%) of AEs requiring modification				
Number (%) of Participants changing therapy regimen due to AE			Difference (95% CI)	P-value
Total number (%) of AEs requiring modification as directed by physician				
Number (%) of Participants changing therapy regimen as directed by physician due to AE			Difference (95% CI)	P-value

[1] 95% confidence interval calculated using the Newcombe-Wilson method without continuity correction. The difference is STOP Taking – KEEP Taking.

[2] The p-value is obtained from the Fisher's exact test. Included in Final Report only.

Table 4.11. Respiratory Adverse Event Overview (ITT population)

The total number of adverse events within the respiratory, thoracic and mediastinal disorders system organ class (Respiratory AEs) is presented in this table overall and by FEV1 (% predicted) category at Week 0 (Visit 1). All events occurring from randomization (Visit 1) through the end of follow-up are included. This table includes both serious and non-serious adverse events within the respiratory, thoracic and mediastinal disorders system organ class.

	STOP Taking (N=x)	KEEP Taking (N=x)	
All Participants, n (%)			
Total follow-up (weeks)			
Total number of Respiratory AEs			
Respiratory AE rate [1]			Rate Ratio (95% CI) [2]
Avg. number of Respiratory AEs per person			
Number (%) of participants with at least one Respiratory AE			Prop. Diff (95% CI) [3]
FEV ₁ (% predicted) <70%, n (%)			
Total follow-up (weeks)			

	STOP Taking (N=x)	KEEP Taking (N=x)
Total number of Respiratory AEs		
Respiratory AE rate [1]		Rate Ratio (95% CI) [2]
Avg. number of Respiratory AEs per person		
Number (%) of participants with at least one Respiratory AE		Prop. Diff (95% CI) [3]
FEV ₁ (% predicted) >=70 to <90%, n (%)		
Total follow-up (weeks)		
Total number of Respiratory AEs		
Respiratory AE rate [1]		Rate Ratio (95% CI) [2]
Avg. number of Respiratory AEs per person		

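### For the lower lung function cohort, the SAP drops the protocol's count of STOP participants who restart hypertonic saline, and its non-adherence measure misses most 5 to 12 day restarts that carry no adverse-event action

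*SAP*

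**What the plan says.** Protocol 14.5 lists three descriptive safety summaries for the LLF cohort: change in FEV₁ % predicted, AE rates, and the proportion "of subjects re-initiating therapy in the discontinuation arm". The third concerns STOP only. It carries no minimum duration and no AE condition.

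SAP 3.2.13 keeps the first two and puts in third place the "proportion of participants non-adherent to assigned therapy after randomization", as a difference between arms. It then defines the term: "Non-adherence will include definitions based on three distinct outcomes: a change action relative to assigned treatment following an adverse event", and in addition "<70% adherence overall post-randomization, and <70% adherence in the last 2 weeks prior to Week 6".

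SAP 3.2.13 does not restate how adherence is calculated. Table 3.3, footnote 1, does: adherence is 100 × Y/X, where "X is the number of days participant submitted the questionnaire and Y is the number of days participant followed treatment assignment". The same formula serves both arms. For the last-2-weeks rows, footnote 4 adds: "Excludes participants who withdrew prior to the end of the window for Week 6 or had no submissions in the last 2 weeks period".

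AE-linked changes are also tabulated elsewhere. SAP 3.2.4 states: "The number and percent of participants changing their assigned therapy due to an adverse event is summarized by intervention arm". Tables 4.5 and 4.10 explain a change as "participants restarting hypertonic saline therapy in" the STOP arm and as stopping it in the KEEP arm. Tables 3.3, 4.5 and 4.10 are not among the exhibits excluded from the LLF reports.

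**The concern.** The protocol measure and the SAP measure count different events. The protocol asks how many people told to stop went back on the drug. The SAP asks how many people in either arm departed from assignment, either through an AE-linked change or by enough days to fall below 70%. A STOP participant who resumes hypertonic saline for a week with no AE action recorded is a re-initiation under the protocol's words, but may be adherent under the SAP.

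No other SAP exhibit fills the gap. The general safety endpoint in Protocol 5.2, any temporary or permanent change of assigned regimen, would have caught such restarts. SAP 3.2.4 narrows it to changes due to an AE, and the SAP's table of changes records that narrowing. Table 3.3 gives the mean, median and range of adherence and the counts at 70% or more, but not the number with any use. Protocol 11.1 keeps in the study participants who alter their regimen for any reason, so restarts without an AE will be observed.

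Protocol 14.7 says the cohort, about 60 per arm, is recruited to look at the safety of discontinuing hypertonic saline. At that size each uncounted restart moves the STOP percentage by 1/60, or 1.7 points.

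**Working it through.** The documents state no figure for this measure, so there is none to reproduce. The check converts the 70% rules into days and asks which restarts they catch.

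**Inputs.** Follow-up is 42 days, with a ±3 day window at Week 6 (Protocol Appendix 2). The final window is taken as 14 days. Adherence is Y/X over submitted diary days (SAP Table 3.3). Assumptions: complete diary, one continuous restart, start day uniform over follow-up, no AE action recorded.

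**Thresholds.** With k on-drug days in STOP:
- Overall: (42 − k)/42 < 0.70 requires k > 12.6, so at least 13 days.
- Last 2 weeks: (14 − k)/14 < 0.70 requires k > 4.2, so at least 5 days.

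**Share uncounted.** A restart of L days can begin on any of 43 − L days. For L from 5 to 12 it cannot reach 13 days, so it counts only if at least 5 of its days fall in days 29-42. A restart beginning on day d ends on day d + L − 1, so this requires d + L − 1 ≥ 33, that is d ≥ 34 − L. The uncounted share is therefore (33 − L)/(43 − L).

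| Restart length | Uncounted |
|---|---|
| 4 days or fewer | all |
| 5 days | 28/38 = 74% |
| 7 days | 26/36 = 72% |
| 10 days | 23/33 = 70% |
| 12 days | 21/31 = 68% |
| 13 days or more | none |

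A restart kept up to Week 6 counts if begun by day 38, so 4 of 42 start days are missed.

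**Sensitivity.**
- 45 days of follow-up: 71-76% uncounted for 5 to 12 days.
- 39 days: 67-71% for 5 to 10 days, and restarts of 12 days or more always count.
- 13-day final window: 4-day restarts move from all uncounted to 29/39 = 74%.
- About 70% diary completion: the thresholds become 10 of 30 submitted days, or 4 of 10 in the last 2 weeks.

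**Allowing for AE-linked restarts.** If a share s of 7-day restarts has an AE action, the SAP's AE definition counts those, and the overall uncounted share is 0.72 × (1 − s): 72% at s = 0, 36% at s = 0.5, 0% at s = 1. The documents do not give s.

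**Between-arm difference, 70% definitions only.** In KEEP the same thresholds are met by 13 skipped days of 42, or 5 of the last 14. As an assumed illustration with 60 per arm, suppose 12 STOP participants (20%) each take a 7-day restart without an AE action. About 12 × 10/36 = 3.3, say 3, are counted (5%). With 0, 3 or 6 KEEP participants below 70% (0%, 5%, 10%), the STOP − KEEP difference is about +5, 0 or −5 points for the same STOP experience.

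**Withdrawals.** If the last-2-weeks definition uses the Table 3.3 denominator, a STOP participant who restarts and then withdraws early is not assessed under it.

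**The case against.** A reader might infer that the SAP measures only adherence below 70%, so that most short restarts of every kind are lost. The documents do not support that. The AE definition has no threshold and counts an AE-linked restart of any length. Protocol 2.1 mentions restarting a stopped medication in the setting of an AE, so these are arguably the restarts closest to a safety signal. A restart without an AE in an open-label trial may be habit or preference, and nothing in the documents makes every restart a sign that stopping was not tolerated.

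A reader might also infer that poor KEEP adherence hides the STOP result. It does not: results are shown by arm, and Tables 4.5 and 4.10 keep restarting and stopping apart. Only the difference under the two 70% definitions is affected.

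Nor is the substitution a breach. Protocol 14.1 lets the SAP modify the analysis plan, and 14.2 leaves LLF details to it. Protocol 14.5 introduces its list as differences between arms, which gives two-arm reporting some basis. It sets no minimum duration either, so isolated use need not amount to re-initiation, and sustained restarts are largely caught.

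All of this stands, and it narrows the point. It does not supply the count the protocol named. The LLF row in the SAP's table of changes says that analysis descriptions were added and a subset of analyses chosen. It gives no reason for dropping the re-initiation proportion.

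**Conclusion.** The point holds in a limited form. The SAP omits a protocol-named safety summary for the LLF cohort, without a recorded rationale, and no other exhibit gives the any-reason proportion of STOP participants who restarted. The loss is confined to restarts without an AE action: about 68-74% of single restarts of 5 to 12 days, and all of 4 days or fewer. Those figures rest on a complete diary, a uniform start day and 42 days of follow-up. The loss across all restarts cannot be stated, because neither restart lengths nor the AE-linked share is given. The between-arm difference under the 70% definitions mixes unlike events and should not be read as a safety contrast.

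The cohort is exploratory and outside the primary analysis, so no primary conclusion is affected. The change is still worth making, because safety of discontinuation is what this cohort is for.

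**What to change.** In SAP 3.2.13, add the number and percent of STOP participants re-initiating hypertonic saline for any reason after randomization, from the daily diary or the concomitant-medication record, with a 95% confidence interval. Split it by with or without an AE action and by temporary or permanent. Show the number of on-drug days beside it, so that isolated single-day use can be told from re-initiation. Keep the AE-linked change summary as it is. Present the below-70% rows by arm as an adherence summary rather than as a safety difference. Record the change and its reason in the SAP's table of changes.

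The cost is one extra row in the LLF report, from data already collected, plus wording. The drawback is that isolated uses will appear in the row, which is why the on-drug days are needed.
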